Maraviroc to Augment Rehabilitation Outcomes After Stroke (MAROS)

NCT03172026

August 1, 2019

Maraviroc To Augment Rehabilitation Outcomes After Stroke (MAROS) Protocol

Version August 1, 2019, revised

[name], et al.

Background

After stroke, the combination of progressive skills practice in an adequate dose, exercise for fitness, and reduced sedentary time will augment motor and cognitive outcomes.

Sensorimotor and cognitive improvements after stroke often reach a general plateau by approximately 12 weeks after onset, however. Drugs that might enhance learning or neural repair, as well as other molecular and synaptic adaptations that occur during skills training and fitness exercise, might extend that recovery curve, although to date only fluoxetine has given any hint of this. Most trials have tested agents that modulate neurotransmitters. Several very recent preclinical experiments and observational studies in patients after stroke suggest that the commercially available medication, Maraviroc, may augment skills learning during rehabilitation training especially during the first three months after onset, by acting on unique molecular components for novel learning.

The C-C chemokine receptor 5 (CCR5) is a seven-transmembrane G protein-coupled receptor that mediates HIV virus cellular entry. Individuals who are homozygous for a 32 base pair deletion in the CCR5 gene (CCR5 Δ 32), and subsequently do not express functional CCR5, are highly protected from infection with R5 HIV-1. The receptor is expressed in microglia, astrocytes and neurons in many regions of the brain. [name] at UCLA postulates that this receptor is involved in learning and memory. In a series of elegant experiments, he showed 1) CCR5 deficiency results in enhancements in hippocampal learning and memory and in experience-dependent sensory plasticity; and 2) CCR5 overexpression leads to learning and memory deficits. Decreasing the function of CCR5 increases MAPK/CREB signaling, long-term potentiation, hippocampus-dependent memory, and neocortical experience-dependent plasticity. Ligand binding to CCR5 is known to modulate several parallel signaling cascades implicated in learning and memory, including the suppression of adenylyl cyclase, as well as the activation of the PI3K/AKT and P44/42 MAPK signaling. These findings support the application of brain permeable CCR5 antagonists, not only as a combination drug in antiretroviral therapy, but also as a treatment for cognitive deficits caused by HIV. In addition, the studies suggest that the receptor is a novel target to augment learning and memory in those with cognitive and motor deficits in relation to training.

Given the potential for Maraviroc to augment rehabilitation training, we will carry out a trial of Maraviroc in patients with disabilities severe enough to have required inpatient stroke rehabilitation and, based on our preclinical data, who can start the drug intervention within 6 weeks of stroke onset. We plan a parallel group, randomized controlled pilot trial at three sites, UCLA SOM, Yale University SOM in New Haven, and Burke Neurological Research Institute in White Plains, NY, to gather enough entries in a shorter time and to better generalize the results of this phase II/III pilot trial. We will compare usual post-stroke care plus placebo versus Maraviroc given for 8 weeks in 60 participants (up to 66 to account for dropouts). The primary outcome measurements will be gains in walking and functional use of the affected upper extremity, continuously monitored remotely, as well as formally assessed at 4 and 8 weeks after initiating the drug and at 6 months (primary endpoint) post stroke onset. To try to maximize the amount of practice that is most relevant to the primary outcome measurements and determine whether or not Maraviroc can enhance the effects of training, as hypothesized, all participants will be monitored by mobile health devices we developed and will receive weekly encouragement, based on device data, to walk, reduce sedentary time, and reach and grasp in the home in between usual care therapies. The amount of use of these telerehabilitation devices will be a nested substudy of feasibility.

We will look for a behavioral marker of the potential effect of Maraviroc by testing each subject while on and off the assigned medication with several commonly used neuropsychological tests of motor and hippocampal learning.

The trial will be registered at ClinicalTrials.gov with ethical approval from the UCLA medical IRB.

Hypothesis 1: Subjects who take Maraviroc plus outpatient and home-based rehabilitation therapy managed remotely will improve significantly more in the primary outcomes of walking speed and upper extremity function by the Action Research Arm Test (ARAT) compared to the placebo drug group at the 6-month post stroke assessment.

Hypothesis 2: The feasibility of home-based telerehabilitation practice will be revealed by the finding that at least 75% of all participants will have achieved compliance for at least 150 minutes of walking and 100 minutes of reach and grasp practice weekly.

Methods

Consent Process:

Participants will be identified from the inpatient stroke rehabilitation admissions to the UCLA affiliated California Rehabilitation Institute (CRI) and from referrals to the Burke Neurological Research Institute in NY and to the Stroke Service in the Department of Neurology

at the Yale University SOM. The Burke and Yale sites will have their own IRB reviews managed by the PIs.

Patients at CRI must check a box that is in the content of their admission papers to be willing to be contacted about research. The CRI Research Committee will let investigators know about those patients who opt in to be contacted and carry the diagnosis of stroke. After a brief chart review of this group, potentially eligible participants who are still at CRI or were discharged in less than 2 months since onset of stroke will be contacted by Drs. [name] or [name] to hear about the aims of the trial and gauge interest, preferably with a significant other present. If the potential subject wishes to learn more, one of these physicians will discuss the trial in detail and begin the process of Informed Consent. Potential participants who are still CRI inpatients may wish to defer a decision until the time of discharge or within the first two weeks after discharge from CRI. We do not plan any interaction with potential participants other than in their private room at CRI or in an outpatient neurology clinic room at UCLA.

In addition, a flyer (submitted) will be posted in the lobby and on the stroke unit at the California Rehabilitation Institute (CRI). The flyer will also be given to physicians to hand to their possibly eligible patients.

Eligibility:

Inclusion criteria include transfer to inpatient rehabilitation within 4 weeks of stroke onset; single ischemic or subcortical hemorrhagic infarct; age >30 years and <86; at the time of randomization, hemiparesis with 4/5 or less strength at the shoulder flexors and at least 3 finger extensors, and the hip and ankle flexors and extensors, as well as a Functional Independence Measure (FIM) score for ambulation ≥ 3 to walk at least 10 steps; caregiver available for at least two hours a day for practice and transportation when needed; adequate language skills to read and understand the Informed Consent and retain information during daily therapies.

Exclusion criteria include prior stroke with persisting motor impairment or disability; limited resources or illness that will not enable a return to living outside of a facility; any medical condition that had limited daily physical activity to walking no more than 2 blocks outdoors prior to the stroke (e.g., claudication, congestive heart failure or lower extremity pain); history of dementia or MMSE score <24; history of hepatitis or elevated hepatic transaminases or bilirubin; history of renal insufficiency or serum creatinine over 1.6; and cancer or other chronic illness that makes 3-year survival unlikely or will detract from the ability to carry out exercise and skills practice.

Randomization:

Participants will be assigned to the control or experimental group using a 1:1 computer-generated randomized allocation schedule in the REDCap clinical database. Assignment (for both research sites) occurs automatically upon the entry of eligibility criteria.

All members of the research team and the subjects will be blinded as to allocation. The study statistician and the rest of the Safety Committee will have access to the assignment if necessary (e.g., adverse drug reaction).

Each site will enter 20-25 subjects, approximately half into each of the trial arms. Entries will be accomplished within 30 months with follow-up assessments and data analyses by the end of 36 months.

Baseline Studies:

We will collect age, gender, body mass index, ethnicity, living place, work status, caregiver support, date of stroke, date of transfer for inpatient rehabilitation, lesion type (TOAST) and location, personal risk factors for stroke, medications, and FIM for level of pre-stroke walking and ADLs. We will measure the National Institutes of Health Stroke Scale (NIHSS), British Medical Council manual muscle exam for eligibility, motor FIM score, 10-m

walking speed, 6-min walking distance, a video-recorded assessment of upper extremity kinematics that does not show the subject's face, and Action Research Arm Test (ARAT). We will record the average two blood pressures and heart rates on the day of entry and the most recent HbgA1c and lipid panel, liver function tests, creatinine/BUN, and MRI/CT imaging results from the inpatient rehabilitation medical record. If liver function tests or creatinine cannot be found, the tests will be obtained at the outpatient research site as a cost to the study. [name] will review each imaging study to localize the relevant stroke lesion by consensus. An email address and phone number for the patient and a close contact will be kept separate from the clinical database by the coordinator.

Interventions:

Maraviroc: Medications are often in flux during inpatient rehabilitation, so Maraviroc or placebo will be started within two weeks of discharge, which most often will occur from 4-6 weeks after stroke onset. A 1-month supply of capsules will be handed to participants after the Consent has been signed, baseline measurements obtained, and randomization assigned, usually on the same day. The second 1-mo supply will be provided during a scheduled interim measurement assessment at UCLA near the end of the 4th week on medication. Pill counts will be taken on the returned bottle. Participants will take either *Maraviroc or a placebo at a dose of 300 mg at 6-8AM*. The capsules will be supplied by the UCLA, Burke and Yale pharmacies to each respective site and used under an IND and IRB protocol as required by each institution.

Based upon Pfizer's reports on premarketing and post marketing studies of Maraviroc and our review of the literature, no dose adjustment is necessary in patients with even mild-to-moderate renal impairment. The drug does not affect the QT interval. At high doses (600mg or more), it may induce orthostatic hypotension, so it is recommended that *users who also take an anti-hypertensive medication be asked about symptoms of orthostatic hypotension*. Of note, 8% of patients in active and placebo drug groups described orthostatic symptoms in a large trial. In HIV trials, 1.3% of subjects had cardiovascular events, more than in the placebo group, but the link to the drug was unclear and symptoms occurred only in those with known cardiac disease. Also, no greater incidence of infection, rash or other CNS symptoms was noted in these subjects. An occasional Stevens-Johnson syndrome and drug rash with eosinophilia and systemic symptoms did occur (seen only in post marketing surveillance, not in controlled trials), so *complaints of rash, fever, joint or muscle aches, blisters, facial edema, etc. will be part of our weekly phone call surveillance plan*. Participants will be told to stop their medication immediately should such symptoms occur and their physician notified. Of note, St John's wort should not be used with the medication since it decreases the concentration of Maraviroc

The drug is metabolized by the liver, so using it in persons with more than mild hepatic disease, especially in the presence of a CYP3A inhibitor, would have to be closely monitored; our participants will be free of hepatic, as well as renal impairment. The recommendation from the FDA is to obtain liver function tests prior to starting the drug and again should symptoms such as rash or hepatitis occur. This rather rare adverse reaction tends to occur at about one month after starting the medication (in less than 4% on the drug or placebo) , so *we will obtain a bilirubin and transaminases at the planned 1-month follow up.*

Adverse events related to the medication assignment, to rehabilitation practice or to other causes will be adjudicated by the Safety Committee with input from the PI.

Rehabilitation therapy: All participants will have routine outpatient or home health physical and occupational therapy after inpatient discharge as prescribed by their physicians. Each group will be contacted weekly by phone by UCLA staff only to help maintain interest in the trial, count the number of usual care physical and occupational therapy completed, assure use of the assigned medication, ask about possible adverse reactions, and to encourage them to be active. The UCLA coordinator will obtain this information and provide the feedback using a

standard script and checklist.

A unique aspect of this trial is a telerehabilitation component that aims to give feedback to all participants to practice with the affected arm and walk daily. All participants will be asked to wear an ankle sensor (Fitbit) that downloads to a computer we supply to each subject. We record lower extremity activity, including walking and cycling. Data includes daily sedentary and active time, walking speed and distance. The walking data is sent to a HIPAA compliant cloud server provided by a commercial company, FitaBase. The coordinator at each site will show each study subject and caregiver how to put on and charge the sensors. At the weekly call, participants will be reminded to try to build up to walking at least 3 times a day for at least 10 minutes per bout and reduce sedentary time. Behavioral modification techniques that we have been using successfully, based on sensor data, will be employed. All such feedback will be provided by the UCLA study group.

Participants will also be given a LEAP Motion Controller device that sits in the bottom of a 12x18" box covered by a plastic lid. This simple system enables us to monitor practice of reaching and grasping with the affected upper extremity in the home. At the weekly call from a UCLA study staff person, they will be encouraged to perform 20 minutes daily of reach, grasp and pinch actions with small common items and practice bringing the affected hand to the mouth. Items will be moved from one corner of the rectangular top to another in a fixed sequence. A unique feature of this trial is that we will have ground truth about how much they did practice, which may enable a dose-response and responder-nonresponder analysis. For example, if a subject is taking the active medication, but never practices, outcomes may be less positive than for the person who does practice as prescribed.

A data manager at UCLA will review all incoming data from the 3 sites for completeness and quality, as well as ensure proper use of the systems (e.g. make sure devices are charged regularly, automatic data uploads occur without problems, and practice data are processed correctly). The study staff at each site will assist the UCLA staff to help solve technical problems with the equipment and interact with subjects around difficulties in patient participation. At the weekly call by UCLA staff, participants will be queried from a script about any possible medical complications. Such potential adverse events will be immediately reported to [name] who will contact his participants or contact the local PI at Burke or Yale to interview their subjects and then report back to [name].

Outcome Measurements:

The primary outcomes will be a timed walking speed over 10 meters by the blinded physical therapist and the ARAT for UE function performed by the blinded therapist. These will be obtained at baseline, then after 4 weeks on assigned medication, within 5 days of the last medication dose (8 weeks) and again at 6 months post stroke onset.

Secondary outcomes obtained at the end of drug treatment and at 6 months after stroke onset by the blinded observer will include the Fugl-Meyer Motor Assessment score for both lower and upper extremities, clinic-based 3-min walking distance, and the Stroke Impact Scale score related to quality of life. We will also assess for satisfaction and self-efficacy for practice and exercise (see Table). Exploratory studies will examine dose of practice based on LEAP data (duration, number of repetitions of reach and grasp of objects) and for walking (total daily walking practice time, sedentary time, and walking bouts of more than 5 minutes), and self-ratings about self-efficacy for exercise.

Statistical Analyses:

A recent observational trial (Lohse and Lang, 2016) found that walking speed increases at 0.1m/s per month and the ARAT increases by 2.9 points monthly within the time frame as this trial.

For the walking speed outcome, the evaluable sample size of 30 in each group will have 80% power to detect a difference in means of -0.206 (m/s), the difference between an assumed usual care walking speed of 0.51 (SD=0.28) and an assumed intervention group mean walking speed of 0.716. This assumes that the common standard deviation in the two groups and a two group t-test with a 0.05 two-sided significance level. The estimates for the mean and standard deviation for walking speed come from the LEAPS RCT (Duncan, N Engl J Med, 2011). We plan to enroll 66 patients to account for an expected 10% drop-out rate. The t-test used for the power calculation is a simplification of the mixed effects analysis plan for the primary endpoints.

For the ARAT sum score, analysis is based on a statistical power of 80% with an alpha of 5% for detecting a meaningful difference of 6 points, i.e., a 10% change, which has been suggested by several completed trials. In a stroke trial, the standard deviation was 8 points measured at 2 weeks post stroke. Again, a sample size of 60 plus 10% dropout rate should suffice.

Primary Analyses: As appropriate, t-tests, Wilcoxon rank sum, or chi-square tests will be employed to evaluate differences in baseline clinical characteristics between trial participants. Using the mixed effects model for *Hypothesis 1* should provide greater power than the t-test as it will account for the repeated observations of the endpoints over time. For *Hypothesis 2*, we will look at one aspect of the feasibility of home-based practice as the ratio of those who achieve at least 150 minutes of weekly walking (composed of bouts that exceed 5 minutes) and 100 minutes of weekly upper extremity practice using the LEAP with the whole group as the denominator. We anticipate that >75% will achieve this by the end of the intervention, based upon our preliminary studies using these devices in a chronic hemiparetic stroke population.

Secondary Analyses: Secondary outcomes listed in the Table will be evaluated using t-tests, Wilcoxon rank sum tests, or chi-square tests as appropriate. One planned secondary analysis will compare outcomes based on whether or not participants can extend their wrist and at least 3 fingers at least 5 degrees at time of randomization, to assess for possible differences in drug responses between those with higher compared to lower levels of initial motor control. Another will compare outcomes in those who achieve the practice goals of Hypothesis 2 to those who do not in relation to drug assignment. We will not likely have enough subjects to do more than look for interesting potential future hypotheses.

Safety Committee:

A Safety Committee will serve both research sites. It will include the study statistician, a physician and an allied health clinician with training in stroke rehabilitation. It will meet before the start of the trial, every 6 months, after the first 10 subjects have completed the 2-month drug intervention, and as needed (e.g., serious adverse reaction).

Confidentiality:

All data will be entered from the study sites at UCLA, Yale and Burke into the RedCap database that will be monitored at UCLA by the study statistician for completeness. All materials related to the trial for UCLA entries will be stored in a locked cabinet in a locked room by the coordinator.

References

Dobkin BH. A Rehabilitation-Internet-of-Things in the Home to Augment Motor Skills and Exercise Training. *Neurorehabil Neural Repair*. 2016 Nov 23. pii: 1545968316680490.

Table. Measurement tools and testing schedule

Category	Test	Schedule		During treatment: at end of 4 and 8 weeks	6 mo outcomes
		Entry	Weekly f/u for 2 mo		
Study Procedures					
Screening	X	X			
Inclusion/Exclusion	X	X			
Informed Consent	X	X			
AE Assessment	X		X		
Demographics	NIH standard	X			
Disability	FIM	X			X
Mobility	10-m walk speed	X		X	X
Upper extremity fx	ARAT	X		X	X
Overall Impairment	NIHSS	X			X
Motor Impairment	Fugl-Meyer motor score	X		End of tx	X
Exercise capacity	6-min walk distance; change in heart rate	X		X	X
Lesion location and subtype	UCLA stroke anatomy form	X			
Walking activity sensors	Duration, distance, speed for bouts; sedentary time	X	X		
Upper extremity practice from sensors	Repetitions, sets	X	X		
Self-reported activity levels pre-stroke	IPAQ	X			
Self-reported activity levels post-entry	IPAQ			X	X
Depression	CES-D	X		End of tx	X
HRQOL	Stroke Impact Scale v3.0	X		End of tx	X
Sensor usage survey	Likert scale			End of tx	
Cognition	MOCA	X			X
Exercise expectations	MOEES	X			X
Social support for activity	Likert scale	X		End of tx	X
Exercise enjoyment	PACES	X		End of tx	X
Self-efficacy for activity	ESFS	X		End of tx	X

To include record of reasons for non-participation.

Adverse events=AE; Center for Epidemiological Studies Depression Scale = CES-D;

Exercise Self-Efficacy Scale=ESFS; Functional Independence Measure=FIM;

International Physical Activity Questionnaire short form=IPAQ; metabolic equivalent minutes per week=METm/wk; Multidimensional outcome expectations for exercise scale=MOEES; Physical Activity Enjoyment Scale=PACES

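### The 6-week limit on starting drug appears in the Aims but not in the eligibility lists, and the CRI recruitment text reaches patients who cannot meet it

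*Combined protocol and SAP*

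**What the plan says.** **Stated population.** The Aims, citing the preclinical data, describe patients "who can start the drug intervention within 6 weeks of stroke onset".

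**Listed criteria.** The Eligibility section times one event against the stroke: "Inclusion criteria include transfer to inpatient rehabilitation within 4 weeks of stroke onset". The exclusion list has no timing rule. Under Randomization, "Assignment (for both research sites) occurs automatically upon the entry of eligibility criteria".

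**Recruitment at CRI.** Under Consent Process, "potentially eligible participants who are still at CRI or were discharged in less than 2 months since onset of stroke will be contacted". Patients who are still inpatients "may wish to defer a decision until the time of discharge or within the first two weeks after discharge from CRI".

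**Dosing.** The Interventions section explains that "Medications are often in flux during inpatient rehabilitation", and so "Maraviroc or placebo will be started within two weeks of discharge, which most often will occur from 4-6 weeks after stroke onset".

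**Data and endpoint.** Baseline Studies collects "date of stroke, date of transfer for inpatient rehabilitation". The primary endpoint is at 6 months counted from the stroke (Aims; Outcome Measurements), while the 4- and 8-week visits are counted from the start of drug.

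**The concern.** The Aims give a time limit with a biological reason, but the section that site staff use to decide who enters does not repeat it. It does carry a different limit, on rehabilitation transfer, which says nothing about when drug starts. The recruitment and dosing text also runs on a longer clock than 6 weeks. Followed as written, the listed criteria admit patients whom the Aims leave out.

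At stake is which population the trial studies. The Background ties the expected benefit to the early period after stroke, so start time is part of the hypothesis. Because the endpoint is anchored to the stroke and treatment is anchored to discharge, a later start also changes the interval between the last dose and the primary assessment.

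**Working it through.** The plan derives no figure from the 6-week limit, so there is none to reproduce. The check compares time windows. Conversion (my assumption): 1 month = 365.25/12/7 = 4.348 weeks, so 2 months = 8.70 weeks (8.0 if read as eight weeks) and 6 months = 26.09 weeks.

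**1. Do the lists imply 6 weeks?** No. The inclusion list caps transfer at week 4. First dose follows discharge, and no criterion caps length of stay. A patient transferred at week 4 passes week 6 after an inpatient stay of 6 − 4 = 2 weeks.

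**2. Who is approached but cannot comply?** Drug starts after discharge, so discharge after week 6 means a start after week 6. The CRI contact window for discharged patients closes at 2 months. The band is 8.0 − 6 = 2.0 weeks to 8.70 − 6 = 2.70 weeks wide.

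**3. What does the two-week dosing allowance add?** Latest start = discharge + 2 weeks.

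| Discharge (weeks after stroke) | Latest start under the allowance |
|---|---|
| 4 | 6 |
| 5 | 7 |
| 6 | 8 |
| 8.0 to 8.7 | 10.0 to 10.7 |

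Only discharge by week 4 guarantees compliance when the whole allowance is used. The Interventions sentence can be read so that the usual 4-6 weeks describes discharge (starts up to week 8 are then ordinary) or drug start (most patients then comply). On either reading it gives a usual range and not a cap. The last two rows are illustrations, not forecasts. The last is not a true maximum, since patients still at CRI are contacted with no time limit.

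**4. What changes with start time?** Weeks off drug before the endpoint = 26.09 − (start + 8).

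| Start week | Last drug week | Weeks off drug before the endpoint |
|---|---|---|
| 4 | 12 | 14.1 |
| 6 | 14 | 12.1 |
| 8 | 16 | 10.1 |
| 10.7 | 18.7 | 7.4 |

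Baseline level is also likely to shift with start time. Statistical Analyses quotes recovery of 0.1 m/s and 2.9 ARAT points per month. If that is linear (my assumption), a 2-week difference in start is 2/4.348 = 0.46 month, or about 0.05 m/s and 1.3 ARAT points. A 4.7-week difference (week 10.7 against week 6) is 1.08 months, or about 0.11 m/s and 3.1 points. The planned differences are 0.206 m/s and 6 points. These shifts apply to both arms.

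**5. Is the power statement affected?** It takes no input on start time. With 30 per arm, a difference of 0.206 and an SD of 0.28, the standardized difference is 0.206/0.28 = 0.736. The two-sided 5% t-test then has power 0.800, which matches the plan. Adding the limit leaves this unchanged.

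**The case against.** The strongest reply is that the limit is already in the protocol. The Aims sentence is written as a statement of whom the trial will treat, and the inclusion list need not be exhaustive. The Background states another entry rule, on interacting drugs, that is also missing from the lists. A contact window decides who hears about the trial, not who enters it. Date of stroke is collected at baseline, and baseline, randomization and dispensing usually fall on one day, so staff could check the limit before assignment. The REDCap fields are not shown, so a 6-week check is not ruled out.

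Much of this stands. It means that late randomization is possible but not established. It does not remove the gap: no documented step applies the limit, and assignment follows from the eligibility entry. If 6 weeks binds, the CRI text approaches patients who cannot qualify; if it does not, the Aims misstate the population.

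The reply is also right about the late-start figures. A start at week 10.0 to 10.7 needs discharge just under 2 months, hence an inpatient stay of at least 4.0 to 4.7 weeks given transfer by week 4. It also needs full use of the allowance and no one applying the Aims. The 2-month window is described for CRI only; no referral window is given for Burke or Yale.

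A reader might infer that late starters weaken the drug effect, because fewer of their 8 drug weeks fall in the first three months. The documents do not support that step. The overlap is calendar arithmetic, and a compliant week-6 start already doses to week 14, past three months (13.0 weeks). A later start also shortens the drug-free gap before the endpoint, which could preserve a fading effect. The net direction is unknown.

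**Conclusion.** The point holds as an inconsistency over who may be randomized. The 6-week limit is stated in the Aims and absent from both eligibility lists, and at CRI there is a discharge band of 2.0 to 2.7 weeks in which patients are approached but cannot meet it. Unless the Aims sentence is enforced by a step that the documents do not show, patients outside the stated population can enter. This rests on reading the Interventions text as post-discharge dosing and on converting 2 months to 8.0 to 8.7 weeks; neither choice alters the conclusion.

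Two stronger inferences should not be drawn. One is bias: randomization balances start time between the arms in expectation. The other is a loss of power: the documents give neither the share of late starters nor how the effect varies with start time. The matter is worth correcting before enrolment proceeds, and it does not threaten the validity of the comparison.

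**What to change.** Add one inclusion criterion, first dose no later than 6 weeks after the stroke, and a matching field in the REDCap eligibility form at all three sites, so that automatic assignment cannot proceed without it. Shorten the CRI contact window to patients who can still meet the limit, and make the consent deferral and the two-week dosing allowance subject to it. If later starts are intended, amend the Aims to one justified wider limit and use that limit throughout.

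Also pre-specify weeks from stroke to randomization as a covariate in the primary mixed model. The endpoint is fixed from the stroke while baseline timing varies, even within the limit. The purpose is to account for that variation, not to correct a bias.

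The cost is amendment wording, one REDCap field and one model term computed from a date already collected. A firm 6-week cap would turn away some candidates, including some who transfer near week 4 and stay more than two weeks. That may slow accrual in a 60-patient pilot by an amount the documents do not allow one to estimate. A justified wider limit would reduce that cost.

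### The plan expects about half of each site's patients in each arm, but the stated 1:1 schedule has no site-level restriction to secure that split

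*Combined protocol and SAP*

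**What the plan says.** The allocation plan is in the Randomization section. Patients are assigned from a "1:1 computer-generated randomized allocation schedule in the REDCap clinical database", and "Assignment (for both research sites) occurs automatically upon the entry of eligibility criteria". The section then states: "Each site will enter 20-25 subjects, approximately half into each of the trial arms". Nowhere does the document mention blocks, stratification or minimisation, and nowhere does it call the list simple or unrestricted.

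The Aims describe a "randomized controlled pilot trial at three sites", whereas the Randomization and Safety Committee sections both refer to two sites. The target is 60 participants, with up to 66 enrolled to allow for dropout.

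Under Statistical Analyses, the primary analysis is a mixed effects model with no covariates named. One planned secondary analysis compares outcomes by "whether or not participants can extend their wrist and at least 3 fingers at least 5 degrees at time of randomization". That factor plays no stated part in the allocation.

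**The concern.** A 1:1 ratio gives equal arms in expectation. It controls the split within a site only if the list is restricted within that site, and the plan states a site-level expectation without a site-level mechanism.

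Site may matter for outcome. One site recruits from its affiliated rehabilitation hospital's admissions and the other two from referrals, and outpatient therapy is whatever each patient's physician prescribes. Initial hand function bears on the ARAT, which is a primary outcome. Both factors are known when the patient is assigned.

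With 20 to 25 patients per site, a visible imbalance in either factor would add noise to the arm comparison, invite doubts about a single small trial, and leave the hand-function comparison with uneven cells. The randomization wording also counts two sites where the Aims count three, so a reader cannot infer that three site-level lists exist.

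**Working it through.** **Inputs.** From the document: three sites; 20–25 patients per site; 60 in total; 30 evaluable per arm; difference 0.206 m/s; SD 0.28 m/s; two-sided 0.05. Assumed: exactly 20 per site (3 × 20 = 60) except where stated, block sizes, and the prevalence of wrist/finger extension.

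**The plan's own figure.** For a two-group t-test with 30 + 30, the noncentrality is 0.206 / (0.28 × √(1/30 + 1/30)) = 0.206 / 0.0723 = 2.85 on 58 degrees of freedom. Power is 80.0%, so the stated 80% is reproduced.

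**Simple list.** The number in one arm at a 20-patient site is Binomial(20, 0.5).
- 13:7 or worse: 2 × (sum of C(20,k), k = 0 to 7) / 2^20 = 2 × 137,980 / 1,048,576 = 26.3%.
- At least one of three sites: 1 − (1 − 0.263)³ = 60.0%.
- 12:8 or worse: 50% per site, and 88% for at least one.
- With 22 per site, 14:8 or worse: 29% per site, and 64% for at least one.

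**One centrally balanced list (30:30), not stratified by site.** The number in one arm at a 20-patient site is hypergeometric (60 patients, 30 in that arm, 20 drawn).
- 13:7 or worse: 17% per site, and about 35% for at least one (20,000 simulated trials; a central list in blocks of 4 gives the same to within a point).
- 12:8 or worse: 41% per site, and 68% for at least one.

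**Blocks stratified by site.** A part-filled block of 4 can be out by at most 2, so a 13:7 split (a difference of 6) is impossible. With blocks of 4 and 6 mixed, the limit is 3. An even site total allows only an even difference, so 20 patients split 11:9 at worst.

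| Schedule, 20 per site | 13:7 or worse, one site | At least one of three |
|---|---|---|
| Simple | 26% | 60% |
| Centrally balanced, not by site | 17% | about 35% |
| Site-stratified blocks of 4 | 0% | 0% |

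**Effect on power.** Under a simple list, 60 patients split 35:25 or worse in 25% of trials. At 35:25 the noncentrality is 0.206 / (0.28 × √(1/25 + 1/35)) = 2.81, and power is 78.9%. Averaged over all splits of a simple list, power is 79.3%, against 80.0% at 30:30.

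**Effect on the walking-speed estimate (site effect assumed).** Suppose the arms are 30:30 overall and one site splits 13:7. That site makes up 13/30 of one arm and 7/30 of the other, a gap of 0.20. If its mean is 0.05–0.14 m/s from the others, the unadjusted difference moves by 0.20 × 0.05 = 0.01 to 0.20 × 0.14 = 0.028 m/s. The standard error is 0.072 and the design difference 0.206.

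**Effect of hand function (prevalence and ARAT gap assumed).** With 30 per arm and no stratification, the proportion able to extend differs between arms by 20 points or more in 20% of trials at 50% prevalence, and in 16% at 30% prevalence. If the two groups differ by 8–12 ARAT points, a 20-point imbalance moves the unadjusted difference by 0.20 × 8 = 1.6 to 0.20 × 12 = 2.4 points. That is 27–40% of the 6-point target.

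**The case against.** A reader might infer that the list is plain, unrestricted randomization. The document does not say so. It is silent on restriction, and both the per-site expectation and the assumption of 30 evaluable per arm fit a restricted or site-level schedule as well. The 60% figure therefore belongs to one reading only, and the range in the table is the fair statement.

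A reader might also infer that the plan breaks its own promise. It promises only an approximate half, and even a simple list gives 11:9 or closer at about half of 20-patient sites. What stands is that the split is not secured.

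Nor does the material support a claim of bias. Chance imbalance does not bias a randomized comparison on average or inflate type I error, and the power cost is under one point. Walking speed and ARAT are measured at baseline and analysed in a repeated-measures model, so initial severity is already captured on the outcome scales. The illustrated site shift is well inside one standard error.

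Finally, the case for making hand function a second stratum is weak. Six strata of about 10 patients would be thin, and the plan itself expects too few subjects for its secondary comparisons to do more than suggest hypotheses. That objection is accepted: adjustment suits this factor better than stratification.

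None of this supplies a mechanism for the per-site split or explains the two-site wording.

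**Conclusion.** The concern holds in a limited form. The plan states a per-site balance that its stated method does not secure. With 20 patients per site, the chance that at least one of three sites reaches 13:7 or worse is about 60% for a simple list, about 35% for a centrally balanced list not stratified by site, and zero with site-stratified blocks of 4. Which applies cannot be told from the document.

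The consequence is some loss of precision and a harder result to interpret. The trial's validity is not in question: average power is 79.3% under a simple list against 80.0% at equal arms. The site and hand-function shifts shown above rest on assumed effects and an assumed prevalence, because the document gives none. The change is worth making because it is cheap and delivers the split the plan already expects.

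**What to change.** 1. State the restriction rule. Use permuted blocks of randomly varied size (for example 4 and 6), stratified by site, loaded as the REDCap allocation table. If the existing list already does this, one sentence reporting it is enough.
2. Name site and wrist/finger extension at randomization as prespecified covariates in the primary mixed model. Do not make hand function a second stratum.
3. Reconcile the two-site wording in the Randomization and Safety Committee sections with the three sites in the Aims.
4. The document does not settle whether enrolment has begun. If it has, either apply the new schedule to the remaining patients, or keep the existing list, report how it was generated, and prespecify the two covariates.

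The cost is a new allocation table, slightly more predictable assignments within a site (limited by blinding and by varying the block size), and a few model degrees of freedom. The extension item is needed at randomization anyway for the planned secondary comparison.
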